5. STUDY DESIGN

5.1. Summary of Study Design

This is an open-label, fixed-sequence, single- and multiple-ascending dose, first-in-human (FIH) study to evaluate the safety, tolerability, PK, PD, and efficacy of intravenous ATB200 alone and when co-administered with oral AT2221. The study was conducted in 4 stages and enrolled 4 cohorts as shown in [Table 2](#).

The 4 cohorts in the study are as follows:

- Cohort 1: this cohort was planned to enroll 11 ERT-experienced ambulatory subjects defined as adults with Pompe disease who have been on ERT for 2 to 6 years prior to enrollment and are able to walk at least 200 meters in the 6-minute walk test (6MWT).
- Cohort 2: this cohort was planned to enroll 4 to 6 ERT-experienced non-ambulatory subjects defined as adults with Pompe disease who are wheelchair-bound and unable to walk unassisted and have been on ERT for \geq 2 years prior to enrollment.
- Cohort 3: this cohort was planned to enroll 5 ERT-naïve ambulatory subjects defined as adults with Pompe disease who have never received treatment with ERT and who are able to walk at least 200 meters in the 6MWT.
- Cohort 4: this cohort was planned to enroll 6 to 8 ERT-experienced ambulatory subjects defined as adults with Pompe disease who have been on ERT for at least 7 years prior to enrollment and are able to walk at least 75 meters in the 6MWT. This cohort was added after Amendment 5 to Protocol ATB200-02.

The 4 study stages are as follows:

- Stage 1 is a 3-period, fixed-sequence, single-ascending dose PK study of ATB200 alone. Safety, tolerability, and PK were evaluated following sequential single-ascending doses of 5 mg/kg, 10 mg/kg, and 20 mg/kg of IV infused ATB200 administered 2 weeks apart. Only subjects in Cohort 1 participated in Stage 1.
- Stage 2 is a 2-period, fixed-sequence, single- and multiple-dose PK study of 20 mg/kg ATB200 co-administered with multiple-ascending doses of AT2221. In Stage 2, safety, tolerability, and PK were evaluated following single- and multiple-ascending dose combinations: 20 mg/kg of IV infused ATB200 co-administered with 130 mg of AT2221 administered orally every 14 days (\pm 3 days) for 3 doses, followed by 20 mg/kg of IV infused ATB200 co-administered with 260 mg of AT2221 administered orally for 3 doses. Only subjects in Cohort 1 participated in Stage 2.

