6.2.2.3. Presentation of Post-baseline Safety Data

The results of post-baseline safety analyses, including by-visit results and changes from baseline, pre-defined limits of change (PDLC) as well as concomitant medications, non-drug therapies, study drug exposure, treatment compliance, TEAEs, and TESAEs will be presented by study stage, as follows:

- Stage 1 analyses and results are presented by SAD treatment dose.
- Stage 2 analyses and results are presented by MAD treatment dose.
- Stages 3 and 4 analyses and results (starting from Stage 2 Period 5) are presented by cohort. The columns displayed will be:
 - Cohort 1, Cohort 2, Cohort 3, Cohort 4
 - Pooled ambulatory subjects (Cohort 1 + Cohort 3 + Cohort 4)
 - Total (where Total = Cohort 1 + Cohort 2 + Cohort 3 + Cohort 4)

Note: Safety analyses for Stages 1 and 2 were reported in iCSR-1 and they will not be repeated in this SAP unless there is a change in the underlying data from Stages 1 and 2. The plan is to copy the pertinent summaries from the iCSR-1 into the final CSR.

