6.4.5. Study Day (Relative Day)

The reference start day is defined for Cohort 1 and for Cohorts 2, 3, and 4 as follows:

- For Cohort 1: Visit 9 (Day 85 in Stage 2, Period 5) is considered the reference start day. This is the day of first dose of the 20 mg/kg ATB200 + 260 mg AT2221 co-administration.
- For Cohorts 2, 3, and 4: The study Day 1 in each cohort is the reference start day.

There will be no Day 0. If the date of interest occurs on or after the reference start day, then the relative study day is calculated as: $(\text{date of interest} - \text{date of reference start day} + 1)$.

Note: The appropriate reference start day should be used depending on whether the summary involves Cohort 1 or Cohorts 2, 3, and 4. For example, for Cohort 1, the relative day of the assessment at V12 will be calculated as: date of V12 – 85 + 1 (ie, Day 43).

If the date occurs before the reference start day, then study day is calculated as: $(\text{date of interest} - \text{date of reference start day})$. Thus, days before the reference start day will have a negative day displacement. For example, for Cohort 1, the relative day of the assessment at the efficacy baseline (V2) will be calculated as: date of baseline assessment – 85.

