10.3. Adverse Events

Treatment-emergent AEs (TEAEs) are defined as AEs whose onset occurs after receiving the study medication. Treatment-emergent AEs that occurred during Stages 1 and 2 have been reported in iCSR-1 and will not be repeated here unless the underlying data have changed.

The SAP describes the events that occurred starting from the administration of 20 mg/kg ATB200 + 260 mg AT2221 in Stage 2 Period 5 through Stages 3 and 4. Events which occur more than 30 days after the last dose of study medication will not be considered as treatment-emergent. Adverse events with an unknown date of onset and a stop date after the start of the study period or unknown will be included as TEAEs. Any AE with a start date equal to the date of first dose, where the time of the AE cannot definitively place the start of the AE prior to the first dose, will be considered as treatment-emergent. If any AE records contain only partial dates, these will be handled by imputation as described in Section 10.1.1. All AEs will be provided in data listings, and those that are treatment-emergent will be flagged in the listings.

Adverse events will be summarized using number and percentage as described in Section 6.2.1. Incidence rate of AEs by patient-years of exposure will also be summarized.

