The percentage of subjects with specific treatment-emergent laboratory values (ie, lab values collected after the first dose in Stage 2 Period 5) that meet the PDLC criteria shown in [Table 8](#) by parameter will be summarized altogether (over the duration from first dose in Stage 2 Period 5 through Stages 3 and 4 to the DBL date), not by visit. The incidence rates of PDLCs will be presented. Unscheduled visits will be included in evaluating the PDLC summary.

A listing will be provided of subjects meeting the PDLC criteria. If a subject has at least 1 post-baseline value that meets the PDLC criteria for any lab parameter, then all values of that parameter for that subject will be listed. For the PDLCs, it is possible for subjects to appear in both categories for any parameter.

Table 8: Pre-defined Limits of Change Criteria for Clinical Safety Laboratory Data

Laboratory Test	Parameter for ANY Value and LAST Value
Chemistry	
Albumin	Composite: < LLN and > 25% decrease from BL
Bilirubin	Composite: > ULN and > 25% increase from BL
	Absolute Value: > 2X ULN
Bicarbonate	Absolute Value: < 16 mEq/L
Calcium	Composite: > ULN and > 10 % increase from BL
Phosphorus	Composite: < LLN and > 25% decrease from BL
	Composite: > ULN and > 25% increase from BL
Potassium	Composite: < LLN and > 15% decrease from BL
	Composite: > ULN and > 15% increase from BL
Sodium	Composite: < LLN and decrease > 5 mEq/L or more from BL
	Composite: > ULN and increase > 5 mEq/L or more from BL
Uric Acid	Male: absolute value \geq 624.6 mM
	Female: absolute value \geq 505.6 mM
	Composite: < LLN and > 25% decrease from BL
	Composite: > ULN and > 25% increase from BL
ALT	Absolute Value: > 3X ULN
	Absolute Value: > 5X ULN
	Absolute Value: > 8X ULN
AST	Absolute Value: > 3X ULN
	Absolute Value: > 5X ULN
	Absolute Value: > 8X ULN

Table 8: Pre-defined Limits of Change Criteria for Clinical Safety Laboratory Data (Continued)

Laboratory Test	Parameter for ANY Value and LAST Value
Chemistry (Continued)	
ALT > 3X ULN and Tbili > 2X ULN	Composite: ALT > 3X ULN and Tbili > 2X ULN (with the Tbili elevation > 2 X ULN within 30 days of the ALT elevation > 3X ULN)
AST > 3X ULN and Tbili > 2X ULN	Composite: AST > 3X ULN and Tbili > 2X ULN (with the Tbili elevation > 2X ULN within 30 days of the AST elevation > 3X ULN)
CK	Absolute CK \geq 2X ULN or 2X baseline value
Hematology	
Hemoglobin	Male: absolute value \leq 11.5 g/dL
	Female: absolute value \leq 9.5 g/dL
	Change: \geq 2 g/dL decrease from BL

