10.7. Electrocardiogram Variables

Quantitative ECG results will be summarized for the actual value and absolute change from baseline values using the descriptive statistics described in [Section 6.2.1](#) and reported per the descriptions in [Section 6.2.2.3](#).

Electrocardiogram results for Stages 1 and 2 have been reported in iCSR-1 and will not be repeated in this SAP unless the underlying data have changed. Otherwise, the final CSR will reference the results in iCSR-1. Electrocardiogram data collected during Stage 2 Period 5 through Stages 3 and 4 to the DBL date will be analyzed on the Safety population.

For categorical ECG data, frequency counts and percentages will be presented. The number and percentage of subjects with ECG interpretations (recorded as: Normal/Abnormal, Not clinically significant/Abnormal, Clinically significant) as well as the specific clinical findings for the abnormal ECGs will be presented.

The incidence rates of values exceeding PDLC for ECG intervals defined in [Table 10](#) by parameter will be summarized altogether (over the duration from first dose in Stage 3 to the data cutoff date), not by visit. Unscheduled visits will be included in evaluating the PDLC summary. For the PDLCs, it is possible for subjects to appear in both categories for any parameter. All ECG data, including the interpretation of normal/abnormal and the specific clinical findings for the abnormal ECGs will be presented in data listings.

Table 10: Pre-defined Limits of Change Criteria for Electrocardiogram Values

ECG Parameter	Criteria	
PR interval (msec)	< 120 msec or \geq 210 msec	
QRS duration (msec)	\leq 50 msec or $>$ 120 msec	
QTcB interval (msec)	Change from baseline for QTcB and uncorrected QT: \leq 30 msec or $>$ 30 msec; \leq 40 msec or $>$ 40 msec Absolute post-baseline QTcB and uncorrected QT interval: \leq 450 msec or $>$ 450 msec \leq 480 msec or $>$ 480 msec \leq 500 msec or $>$ 500 msec	
QTcF interval (msec)	Change from baseline for QTcF and uncorrected QT: \leq 30 msec or $>$ 30 msec; \leq 40 msec or $>$ 40 msec Absolute post-baseline QTcF and uncorrected QT interval: \leq 450 msec or $>$ 450 msec \leq 480 msec or $>$ 480 msec \leq 500 msec or $>$ 500 msec	
Ventricular rate (bpm)	A decrease from reference \geq 15 bpm, and an absolute value $<$ 50 bpm	An increase from reference \geq 15 bpm, and an absolute value $>$ 120 bpm

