10.8. Physical Examination

No data on physical examination (PE) during Stages 1 and 2 were available to be reported in iCSR-1. All PE data, including data for Stages 1 and 2 (if available), will be summarized on the Safety population using the descriptions in [Section 6.2.1](#) and presented as described in [Section 6.2.2.3](#).

Both comprehensive physical examinations (CPE) and brief physical examinations (BPE) data collected during Stage 2 Period 5 through Stages 3 and 4 to the DBL will be summarized by body system. The number and percentage of subjects with overall assessment of CPE judged to be normal, abnormal, or not done will be summarized. For both CPE and BPE, the results of the

clinical significance categorized as ‘Clinically significant’ and ‘Not clinically significant’ will be summarized.

Further, the results of the physical examinations will be summarized for subjects who had examination at both baseline and post-baseline. Each site/system will be summarized with respect to being normal, abnormal, or not performed. The number and percentage of subjects judged to have ‘improved’ (ie, changed from abnormal at baseline to normal), ‘worsened’ (ie, changed from normal at baseline to abnormal), or remained unchanged from baseline to each post-baseline visit will be presented.

Supportive data listings will be provided that include the information collected on the eCRF (eg, body system/category, result of the observation [eg, normal, abnormal, or not performed], description of abnormal findings, and any investigator comment). Additionally, for observations related to safety, a listing of subjects with laboratory values, vital signs, and ECG values meeting the PDLCs, as well as abnormal PE values, will be provided (per ICH E3 Section 14.3.4).

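### SAP 10.7 counts ECG limit-of-change incidence from the first Stage 3 dose, contradicting its own ECG analysis period and the laboratory and vital-sign counts, which start at Stage 2 Period 5

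*SAP*

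**What the plan says.** SAP 10.7 gives two periods for ECG data.

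- For the analysis as a whole: "Electrocardiogram data collected during Stage 2 Period 5 through Stages 3 and 4 to the DBL date will be analyzed on the Safety population".
- For the PDLC incidence, later in the same section: "over the duration from first dose in Stage 3 to the data cutoff date".

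The comparable parts of the SAP start at Period 5.

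- Laboratory PDLC incidence (10.4) runs "over the duration from first dose in Stage 2 Period 5 through Stages 3 and 4 to the DBL date". Vital-sign PDLC incidence (10.6) is given the same period in the same words.
- Adverse events (10.3) are described "starting from the administration of 20 mg/kg ATB200 + 260 mg AT2221 in Stage 2 Period 5 through Stages 3 and 4".
- For physical examinations (10.8), "data collected during Stage 2 Period 5 through Stages 3 and 4 to the DBL will be summarized by body system".
- The general presentation rule (6.2.2.3), which names PDLC results among those it covers, says "Stages 3 and 4 analyses and results (starting from Stage 2 Period 5) are presented by cohort". Section 10.7 itself refers to this rule for reporting.

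Period 5 is where Cohort 1 first receives the fixed regimen. The Stage 2 description in SAP 5.1 has the 130 mg combination "followed by 20 mg/kg of IV infused ATB200 co-administered with 260 mg of AT2221 administered orally for 3 doses". SAP 6.4.5 then sets the clock for Cohort 1: "Visit 9 (Day 85 in Stage 2, Period 5) is considered the reference start day".

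**The concern.** The two statements in 10.7 cannot both be followed. A programmer working from the operative PDLC sentence would start Cohort 1 at its first Stage 3 dose, which comes after three doses of the fixed regimen. The SAP gives no reason for treating ECGs differently, and Section 11, which lists changes of method, does not mention one.

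Three things would follow.

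- Cohort 1's first post-baseline ECGs on 260 mg AT2221 with 20 mg/kg ATB200 would be missing from the outlier count. ECGs are scheduled every two weeks in Period 5 (Protocol Table 9) and every three months in Stage 3 (Protocol Table 10). Visits 9 and 11 are serial PK visits, with an ECG before dosing and another at the end of infusion (Protocol 10.2.8).
- ECG incidence would cover a different period from the laboratory and vital-sign incidence reported beside it, with nothing to tell the reader so.
- The Stages 3 and 4 Safety population (SAP 6.1.2) admits a Cohort 1 subject after one Period 5 dose. A subject who stopped during Period 5, if there was one, would be in the denominator with no ECG that could count.

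Change from baseline in 12-lead ECG is one of the primary safety endpoints (Protocol 12.1.1), so the counting period should be unambiguous.

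**Working it through.** **Inputs**

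- First fixed-regimen dose, Cohort 1: Visit 9, Day 85 (SAP 6.4.5).
- Other Period 5 doses: Visit 10, Day 99, and Visit 11, Day 113 (Protocol Table 9).
- First day of Stage 3, Cohort 1: Visit 12, Day 127 (Protocol 10.1.6).
- Cohort 1 size: 11 planned (SAP 5.1), or approximately 10 to 12 (Protocol 8.1).
- ECG scheduled at each of Visits 9, 10 and 11 (Protocol Table 9).
- Cohort 1 safety baseline: last result on or before the start of the fixed regimen in Period 5, that is Visit 9, or Visit 8 if Visit 9 is unavailable (SAP 6.4.1, Table 3).

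**Step 1. Reproduce the SAP's own figure.** Relative day = study day − 85 + 1. For Visit 12: 127 − 85 + 1 = 43. SAP 6.4.5 also gives Day 43.

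**Step 2. Place the three Period 5 doses.**

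- Visit 9: 85 − 85 + 1 = Day 1
- Visit 10: 99 − 85 + 1 = Day 15
- Visit 11: 113 − 85 + 1 = Day 29

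All three fall before Day 43. A count that starts at the first Stage 3 dose therefore omits relative Days 1 to 42 (127 − 85 = 42 days).

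**Step 3. Size the omission.** 3 visits × 11 subjects = 33 subject-visits. For 10 and 12 subjects it is 30 and 36. These are ceilings that assume every subject attended all three visits.

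**Step 4. Allow for baseline.** The pre-dose Visit 9 ECG is the baseline and would not enter a post-baseline count under either wording. At Visit 9, only the recordings after dosing are at issue.

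**Step 5. Cohorts 2 to 4.** Their first dose is in Stage 3, so the start of their counting period is the same under both wordings.

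**Step 6. What it could do to the result.** The documents give no exceedance rate. As an assumption only, take independent visits and a per-visit exceedance probability p. The chance that a subject has at least one exceedance in the three omitted visits is 1 − (1 − p)³:

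| p | 1 − (1 − p)³ |
|---|---|
| 1% | 3.0% |
| 5% | 14.3% |
| 10% | 27.1% |

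For a count of subjects these are upper bounds on the change, because a subject who also exceeds a limit later is counted anyway.

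**The case against.** The best defence is that this is leftover shorthand. Section 10.7 points to 6.2.2.3, which already starts PDLC results at Period 5. SAP 6.1.3 also uses Stage 3 loosely: it defines the Efficacy population by a dose in Stage 3 and then explains that for Cohort 1 this means Period 5. That is probably how the wording arose. But 6.1.3 supplies the explanation and 10.7 does not, and a general rule does not override an explicit, different period in the sentence that defines the count.

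The defence is right that little is lost from the report. The by-visit safety summaries include Visits 10 and 11 (SAP 6.5.1), all ECG data are listed (10.7), and a listing of subjects with ECG values meeting the limits is planned (10.8). The post-dose Visit 9 recordings fall before the first post-baseline window in Table 4 (Day 9 to 22), so they would appear in listings only. The earlier interim report is not a dependable substitute for the count: 10.7 says it reported Stages 1 and 2, but SAP Section 2 says its safety data were mainly those collected before the fixed regimen.

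It is also fair that the study is descriptive with no hypothesis tests, and that 42 days in one cohort is short against 24 months of Stage 3 plus Stage 4.

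**Conclusion.** The inconsistency is real and sits in the operative sentence. Followed literally, it removes up to about 33 Cohort 1 subject-visits (30 to 36 for 10 to 12 subjects), all within the first 42 days on the fixed regimen, from one cumulative descriptive count. This rests on the planned enrolment and on full attendance at Visits 9 to 11. Whether any reported incidence would change is unknown. A per-subject figure changes only if a subject's sole exceedance fell in that span.

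Three stronger readings are tempting, and the documents do not support them.

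- A reader might take the data cutoff date to be that of the second interim report, 13 December 2021, and infer a further loss of about 2.6 years to the planned lock on 24 July 2024. But SAP 10.2 uses the same term generically in the final-report exposure formula, and Section 2 says all study data will be reported, with the long-term analyses running through the DBL. The term most naturally means the end of the data.
- A reader might say that every other safety table starts at Period 5. Stage 1 and Stage 2 tables are carried over separately, and 10.6 ties its time-point summaries of vital signs to Stage 3. The sound comparison is with the laboratory and vital-sign PDLC counts and the general rule in 6.2.2.3.
- A reader might treat all Visit 9 ECGs as lost. The pre-dose one is the baseline.

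**What to change.** In SAP 10.7, replace the parenthesis that defines the ECG PDLC period with the wording of 10.4 and 10.6: "over the duration from first dose in Stage 2 Period 5 through Stages 3 and 4 to the DBL date". Add that for Cohorts 2 to 4 the period starts at Day 1. Changing the end point from data cutoff date to DBL date is for consistency only.

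The cost is one phrase, settled before database lock as SAP Section 2 requires of analysis decisions. No new data, assessments or tables are needed. If the Stage 3 start was intended, 10.7 should say so, give the reason, and have the table state that it covers a shorter period than the laboratory and vital-sign counts.

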10.8. Physical Examination

No data on physical examination (PE) during Stages 1 and 2 were available to be reported in iCSR-1. All PE data, including data for Stages 1 and 2 (if available), will be summarized on the Safety population using the descriptions in [Section 6.2.1](#) and presented as described in [Section 6.2.2.3](#).

Both comprehensive physical examinations (CPE) and brief physical examinations (BPE) data collected during Stage 2 Period 5 through Stages 3 and 4 to the DBL will be summarized by body system. The number and percentage of subjects with overall assessment of CPE judged to be normal, abnormal, or not done will be summarized. For both CPE and BPE, the results of the

clinical significance categorized as ‘Clinically significant’ and ‘Not clinically significant’ will be summarized.

Further, the results of the physical examinations will be summarized for subjects who had examination at both baseline and post-baseline. Each site/system will be summarized with respect to being normal, abnormal, or not performed. The number and percentage of subjects judged to have ‘improved’ (ie, changed from abnormal at baseline to normal), ‘worsened’ (ie, changed from normal at baseline to abnormal), or remained unchanged from baseline to each post-baseline visit will be presented.

Supportive data listings will be provided that include the information collected on the eCRF (eg, body system/category, result of the observation [eg, normal, abnormal, or not performed], description of abnormal findings, and any investigator comment). Additionally, for observations related to safety, a listing of subjects with laboratory values, vital signs, and ECG values meeting the PDLCs, as well as abnormal PE values, will be provided (per ICH E3 Section 14.3.4).

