11.1. Definitions

11.1.1. Adverse Events

An AE is any untoward medical occurrence in a subject administered a pharmaceutical product, biologic (at any dose), or medical device, which does not necessarily have a causal relationship with the treatment. Therefore, an AE can be any unfavorable and unintended sign (including an abnormal laboratory finding), symptom, or disease temporally associated with the use of a medical product, whether or not considered related to the medical product. Adverse events may include the onset of new illness and the exacerbation of pre-existing conditions.

The routine evolution of the disease condition under treatment according to the protocol will be evaluated as part of the disease symptoms assessments. Changes in Pompe disease symptoms must be reviewed by the investigator or a medically qualified sub-investigator and be recorded as “Clinically Significant” or “Not Clinically Significant” in subjects’ source records. Changes in the disease condition may not qualify as AEs. However, if there is a clinically relevant worsening of a sign or symptom of the condition under treatment and the outcome fulfills the definition of an AE, it must be reported as directed in the protocol.

Any AE that begins after the first dose of study medication (ATB200 and/or AT2221) will be considered a TEAE.

Subjects experiencing AEs should be followed until their health has returned to baseline status or stabilized or have otherwise been explained.

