12.1. Endpoints

12.1.1. Primary Endpoints

Safety:

- Identification and counts of TEAEs, treatment-emergent SAEs, including IARs
- Changes from baseline in 12-lead ECG
- Changes from baseline in clinical safety laboratory evaluations: serum chemistry, hematology, and urinalysis
- Changes from baseline in PEs
- Changes from baseline in vital signs
- Changes from baseline in serum CK

PK for subjects from Cohort 1:

- Plasma GAA activity levels and total GAA protein concentration PK parameters: C_{max} , t_{max} , AUC_{0-t} , $AUC_{0-\infty}$, $t_{1/2}$, steady state volume of distribution (V_{ss}), and CL_T for each dose level
- Stage 1: Ratios of plasma GAA activity levels and total GAA protein concentration C_{max} , AUC_{0-t} , and $AUC_{0-\infty}$ for 20 mg/kg versus 5 mg/kg, 20 mg/kg versus 10 mg/kg, and 10 mg/kg versus 5 mg/kg
- Stage 2: Ratios of plasma GAA activity levels and total GAA protein concentration C_{max} , AUC_{0-t} , and $AUC_{0-\infty}$ for 20 mg/kg ATB200 (from Stage 1) versus single-dose 20 mg/kg ATB200 + 130 mg AT2221, and versus single-dose 20 mg/kg ATB200 + 260 mg AT2221
- Stage 2: Ratios of plasma GAA activity levels and total GAA protein concentration C_{max} , AUC_{0-t} , and $AUC_{0-\infty}$ for 20 mg/kg ATB200 + 130 mg AT2221 single-dose versus multiple-dose, and 20 mg/kg ATB200 + 260 mg AT2221 single-dose versus multiple-dose
- Plasma AT2221 PK parameters: C_{max} , t_{max} , AUC_{0-t} , $AUC_{0-\infty}$, $t_{1/2}$, total clearance following oral administration (CL_T/F), and terminal phase volume of distribution following oral administration (V_z/F) for each dose level
- Ratios of plasma AT2221 C_{max} , AUC_{0-t} , and $AUC_{0-\infty}$ for 260 mg single-dose versus 130 mg single-dose, and for 260 mg multiple-dose versus 130 mg multiple-dose
- Ratios of plasma AT2221 C_{max} , AUC_{0-t} , and $AUC_{0-\infty}$ for 130 mg multiple-dose versus 130 mg single-dose, and 260 mg multiple-dose versus 260 mg single-dose

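### The physical-examination change table in SAP 10.8 cannot show deterioration in a body system already abnormal at baseline, and it reports moves between not clinically significant and clinically significant as unchanged

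*SAP*

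**What the plan says.** Protocol 12.1.1 lists "Changes from baseline in PEs" among the primary safety endpoints, and SAP 4.2 carries it as a safety variable.

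SAP 10.8 plans several PE outputs. For subjects examined both at baseline and afterwards, it states: "Each site/system will be summarized with respect to being normal, abnormal, or not performed". Subjects are then counted as improved, worsened or unchanged at each visit. Improved means "ie, changed from abnormal at baseline to normal". The text on worsening runs "ie, changed from normal at baseline to abnormal), or remained unchanged from baseline to each post-baseline visit will be presented". There is no separate definition of unchanged.

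Clinical significance is handled in the preceding paragraph of the same section. For both comprehensive and brief examinations, "clinical significance categorized as ‘Clinically significant’ and ‘Not clinically significant’ will be summarized". No cross-tabulation against baseline is described. The section also provides listings with the result, a description of each abnormality and the investigator's remarks.

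**The concern.** The endpoint is change, and the improved/worsened/unchanged table is the only PE output in SAP 10.8 that summarises change. Its rule does not use clinical significance, although that grading is available and is summarised a few lines earlier.

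This matters most where a system is abnormal at entry. Pompe disease is progressive (Protocol 6.1), and Cohort 2 subjects must be "wheelchair-bound and unable to walk unassisted". Abnormal findings at baseline in the affected systems are to be expected, although neither document reports any. For such a system, a finding that goes from NCS to CS appears under unchanged, and a reader of the table would take that as stability.

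What is at stake is the meaning of the tabulated summary for one named primary safety endpoint. SAP 9.1 plans no hypothesis test, so no error rate, sample size or decision rule is affected.

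**Working it through.** **Inputs.** The states and the definitions of improved and worsened come from SAP 10.8. Unchanged is taken as the remaining category, since the SAP gives it no other meaning. The comparison scale is Normal < Abnormal NCS < Abnormal CS, the same three grades that SAP 10.7 uses for ECG interpretation.

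**Step 1: list every move for one body system.**

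| Baseline | Post-baseline | SAP 10.8 rule | Three-level scale |
|---|---|---|---|
| Normal | Normal | unchanged | unchanged |
| Normal | NCS | worsened | worsened |
| Normal | CS | worsened | worsened |
| NCS | Normal | improved | improved |
| NCS | NCS | unchanged | unchanged |
| **NCS** | **CS** | **unchanged** | **worsened** |
| CS | Normal | improved | improved |
| **CS** | **NCS** | **unchanged** | **improved** |
| CS | CS | unchanged | unchanged |

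**Step 2: count.** The SAP rule gives 2 worsened, 2 improved and 5 unchanged, total 9. The three-level scale gives 3, 3 and 3. They differ in 2 of 9 moves, one in each direction.

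**Step 3: look at abnormal baselines only.** Six moves start from an abnormal system. The SAP rule calls 2 improved, 4 unchanged and 0 worsened.

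**Step 4: what this does to the percentages.** Assume the denominator is all n subjects examined at both times, with k of them abnormal in that system at baseline. Then reported worsened cannot exceed (n − k)/n, and reported improved cannot exceed k/n. With n = 11 (planned size of Cohort 1), the ceiling on worsened runs from 11/11 = 100% at k = 0 to 0/11 = 0% at k = 11. It drops by 1/11, or 9.1 percentage points, for each subject abnormal at baseline. With n = 4 to 6 (Cohort 2), each such subject costs 1/4 = 25 to 1/6 = 16.7 points. These are limits over the whole range of k, not estimates, because the documents do not give k.

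**Step 5: check whether another planned output fills the gap.** The CS/NCS summary gives counts with no link to baseline status, so it does not show who moved. The AE tables in SAP 10.3.1 are organised by system organ class and preferred term and do not give change from baseline by examined body system. The listings hold individual results but do not summarise them.

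**The case against.** The strongest reply is that the safety information is not lost. Protocol 10.2.7, the section on physical examination, says a CS abnormality that is new or has worsened should be reported as an AE. A move from NCS to CS is that kind of event, and it then enters the AE tables by intensity and relationship. Protocol 11.4 also requires worsening of pre-existing complaints to be entered as AEs. SAP 10.8 reports CS/NCS and lists abnormal findings. With cohorts of 4 to 11 planned subjects, individual courses can be read from listings. Muscle and respiratory decline is measured directly by the motor function, muscle strength and pulmonary function tests in SAP 9.4. All of this stands, and it limits the point to presentation.

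Three stronger readings are tempting, and the documents do not support them.

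- *A subject abnormal at baseline can never be recorded as worsening.* The rule works by site or system, so the same subject can be worsened in another system, and the limit belongs to one table.
- *The table is biased toward benefit.* CS to NCS is hidden in the same way as NCS to CS, improved requires a return to fully normal, and a system normal at baseline can never improve. The net direction depends on baseline findings that are not given.
- *Disease-related worsening escapes AE reporting.* Protocol 11.1.1 does say "Changes in the disease condition may not qualify as AEs". Its next sentence requires reporting when a worsening is clinically relevant and meets the AE definition. Some investigator judgement remains, but there is no general exemption.

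**Conclusion.** The point holds for one table. In the SAP 10.8 change summary, a body system abnormal at baseline can be improved or unchanged but never worsened, and partial moves between NCS and CS are hidden in both directions (2 of 9 moves). This follows from the SAP's definitions and rests on one assumption, that unchanged is the residual category. Detection of worsening is largely secured through AE reporting, the CS/NCS summary and the listings. What is missing is a summary of change that can show deterioration in a system already abnormal, for an endpoint that the protocol calls primary.

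How many subjects this would affect cannot be stated. A worked percentage for Cohort 1 or Cohort 2 would rest entirely on assumed baselines. The weight is modest, since the study is descriptive, but the label unchanged would be wrong for a real worsening and the correction is simple.

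**What to change.** In SAP 10.8, replace the two-level rule with a shift of Normal / Abnormal NCS / Abnormal CS from baseline to each post-baseline visit and to the worst post-baseline result. Do this by body system if clinical significance is recorded at that level, and otherwise on the overall assessment; the SAP does not say which applies, so the eCRF must be checked. Count NCS to CS as worsened and CS to NCS as improved. Define unchanged as the same category at both times. Show not performed as a count outside the denominator, in line with SAP 12.2, which already bases percentages on non-missing data. A cross-reference to the AE tables would tell the reader where worsening within CS is reported, because the three-level scale still cannot show that.

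SAP Table 11 drops shift tables for vital signs, laboratory data and ECG but does not name PE, so the change does not conflict with it. The cost is a paragraph of SAP text, one revised table shell and a slightly larger table. No new data are needed if the check confirms that clinical significance is held at the level used.
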